Blood samples (10cc) will be collected from patients at baseline and 3 months for inflammatory cytokine measurement. At the baseline and 3 months subjects will be asked to complete the Minnesota Living With Heart Failure Questionnaire. At the 1 month visit, the patients will be interviewed by the unblinded physician or clinical coordinator to address any issues with TENS administration at home, and to assess their adherence to the stimulation protocol. A schematic representation of the study design is shown in Figure 5.

Data collection and analysis

Data will be collected by study personnel. Patients will be blinded to the treatment allocation, and every effort will be made to conceal from the study personnel the nature of the intervention in each study arm. The patients will be requested to refrain from discussing the details of their treatment with other patients in the clinic and with the physicians, nurses and the rest of clinic staff. The clinical coordinator and a clinic physician who will not participate in any of the other study related assessments will be unblinded to the treatment allocation and will instruct the patients

on the proper use of the device. These study personnel will be designated to address the patients' questions and concerns as well as to record any side effects related to the use of the device. The final data will be pooled and analyzed by the investigators.

Definition of outcomes

The coprimary outcomes at 3 months are 1) the ratio of the early mitral inflow Doppler velocity to the early diastolic mitral annulus velocity (E/e') and 2) global longitudinal strain (GLS). Secondary outcomes include other echocardiographic parameters [early diastolic mitral annulus velocity (e'), left atrial volume index, tricuspid regurgitation Doppler velocity, ratio of early to late mitral inflow Doppler velocity (E/A), global circumferential strain], 6-minute walk distance, quality of life (assessed by the Minnesota Living with Heart Failure Questionnaire). To ensure rigor, analysis and interpretation of the echocardiographic data, the 6-minute walk test data and inflammatory cytokine data will be performed in a blinded fashion.

Duration of participation:

Enrolled patients will participate in the study for 3 months.

Patient enrollment:

A maximum of 72 patients meeting the inclusion criteria and not meeting the exclusion criteria will be enrolled in the study. The enrollment period is expected to last for at least 18 months.

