Data collection and analysis:

The final data will be pooled and analyzed by the investigators.

E. Statistical methods

Markers of inflammation, 6-minute walk distance and echocardiographic parameters will be compared between groups using repeated measures ANOVA, with 2 time points (baseline, 3 months) and 3 terms included in the model (group effect, time effect, group by time interaction). Significant interactions will be followed by time trend analyses stratified by intervention group. Transformations will be used as appropriate to satisfy modeling assumptions. Analyses will be based on the intention-to-treat principle. A separate per-protocol analysis, analyzing data from all patients who adhered to the TENS protocol at least 80% of the time, will also be performed. Sex will be investigated as a biologic variable by including sex, and interactions with sex, in the ANOVA model. Modification by sex will be explored and interpreted cautiously given that the pilot study is not powered to detect modification by sex. Gene expression array data will be analyzed using a Mann-Whitney U test, adjusting for multiple comparisons using the Benjamini-Hochberg method. Statistical significance will be set at $p<0.025$ for the 2 coprimary outcomes and at $p<0.05$ for all other data.

No formal interim efficacy analyses will be performed. Data quality and protocol implementation, as well as adverse events, will be summarized every six months for the DSMB.

Sample size and power calculations:

For purposes of sample size calculations we have simplified the analysis to focus on the difference in the E/e' ratio between the 2 intervention groups. Assuming a mean \pm standard deviation E/e'

ratio 11.1 ± 4.4 ²⁸ and 30% reduction in the LLTS group¹⁹, 72 patients would provide 80% power to detect the specified effect sizes at a two-sided α level of 0.025. The same sample size, under similar assumptions and a baseline GLS 16.1 ± 2.2 , would provide 90% power to detect an absolute 1.8% difference in GLS between the 2 groups.

F. Gender/Minority/Pediatric Inclusion for Research

Participants will be age 18 or older. Race, minority status and gender will not affect enrollment.

G. Human participants

72 participants of any gender/ethnic group, age 18 to 90 will be included.

Inclusion Criteria:

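### Testing each coprimary outcome at a fixed 0.025 is valid, but the Holm procedure has the same 5% family-wise limit, loses no rejection, and gives more power for the second outcome

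*Combined protocol and SAP*

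**What the plan says.** Under Definition of outcomes (Section D): "The coprimary outcomes at 3 months are 1) the ratio of the early mitral inflow Doppler velocity to the early diastolic mitral annulus velocity" (E/e'), with global longitudinal strain (GLS) as the second.

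Section E, Statistical methods, gives the decision rule: "Statistical significance will be set at $p<0.025$ for the 2 coprimary outcomes and at $p<0.05$ for all other data".

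Sample size and power calculations uses the same level. For E/e', "72 patients would provide 80% power to detect the specified effect sizes at a two-sided α level of 0.025". For GLS, the same sample size "would provide 90% power to detect an absolute 1.8% difference in GLS between the 2 groups".

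No step-down or alpha-recycling rule appears anywhere, and no interim efficacy analysis is planned, so the full alpha is available at the final analysis. The documents do not say whether one significant coprimary outcome is enough or both are needed. The 0.05/2 split implies that each can be claimed on its own.

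**The concern.** Under the fixed rule each outcome faces 0.025 whatever the other shows. Once one outcome has been rejected at 0.025, only one hypothesis remains, and it can be tested at the full 0.05 without breaking the 5% family-wise limit. The plan does not use this.

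For example, with p = 0.01 on one outcome and p = 0.04 on the other, the plan can claim only the first, while Holm validly claims both. What is at stake is the claim on the second outcome, meaning whichever has the larger p-value. The chance of a positive result on at least one outcome is not affected.

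If the intention is that both must be significant, the split is not needed at all, because requiring both at 0.05 already controls the error.

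**Working it through.** **Inputs.** From Sample size and power calculations: E/e' "ratio 11.1 ± 4.4" with a "30% reduction in the LLTS group"; GLS SD 2.2 with a difference of 1.8; 72 patients; two-sided 0.025. From Section D: 1:1 allocation, so 36 per arm. *Assumed*, because the documents give no figure: an E/e'-GLS correlation of 0 to 0.5, with 0.8 as an extreme.

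**1. Error of the fixed rule.** 0.025 + 0.025 = 0.05 bounds the family-wise error under any dependence. For independent outcomes it is 1 − 0.975² = 0.0494. The rule is valid.

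**2. Effects and the plan's own power.**
- E/e': 0.30 × 11.1 = 3.33, and 3.33/4.4 = 0.757 SD.
- GLS: 1.8/2.2 = 0.818 SD.
- Two-sample t-test (noncentral t), 36 per arm, alpha 0.025: E/e' 81.9% (plan: 80%), GLS 87.8% (plan: 90%; the normal approximation gives 89.1%). The plan's figures are broadly reproduced.
- At alpha 0.05: E/e' 88.6%, GLS 92.8%. These are ceilings for Holm.

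**3. Holm against the fixed rule.** Holm rejects an outcome if p < 0.025, or if p < 0.05 and the other outcome has p < 0.025. The first condition is the fixed rule, so no rejection can be lost. Simulated pairs of correlated t-tests, 400,000 per setting, 36 per arm, both effects as planned:

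| Correlation | E/e', fixed → Holm | GLS, fixed → Holm | Both, fixed → Holm | At least one, either rule |
|---|---|---|---|---|
| 0 | 82% → 87.8% | 88% → 92.0% | 71.9% → 81.9% | 97.8% |
| 0.3 | 82% → 87.4% | 88% → 91.3% | 73.7% → 82.7% | 96.0% |
| 0.5 | 82% → 87.1% | 88% → 91.0% | 75.3% → 83.6% | 94.5% |
| 0.8 | 82% → 86.7% | 88% → 90.0% | 78.5% → 85.4% | 91.3% |

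**4. Other settings (correlation 0 to 0.5).**
- 32 evaluable per arm (assumed loss of 4/36 = 11%; the plan states no allowance): E/e' 77% → 82-83%, GLS 83% → 87-88%, both 64-68% → 75-78%.
- E/e' effect halved, GLS as planned: E/e' 25% → 34-35%.
- Only one effect real: power for that outcome rises by about 0.1-0.2 points.

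**5. Error under Holm.**
- Both null: any rejection 5.0%, 4.8%, 4.7% and 4.0% at correlation 0, 0.3, 0.5 and 0.8, identical to the fixed rule.
- One effect real, the other null: error for the null outcome rises from 2.5% to 4.3-4.7% (correlation 0 to 0.5), within 5%.

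**6. If both outcomes are required.** Testing each at 0.05 gives joint power of 82-84%, against 72-75% at 0.025 each (correlation 0 to 0.5).

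**The case against.** The strongest reply is that nothing is broken. The plan foresaw multiplicity, controlled it, and powered the trial at the same level. Bonferroni gives simple 97.5% intervals that match the tests and a verdict on each outcome that does not depend on the other. In a pilot, the chance of any positive coprimary result is unchanged, and a p-value between 0.025 and 0.05 would be reported anyway. All of this is true, and it is why the point is an improvement and not a defect.

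A second objection concerns size. The figures use two-sample t-tests, as the plan's own simplification does, but the planned analysis is repeated measures ANOVA. With two time points, the group-by-time test compares changes, and the standardised effect becomes d/√(2(1 − r)), where r is the baseline-to-3-month correlation, which the documents do not give. For assumed r and outcome correlation 0 to 0.5, the gain in the chance of claiming both is about 11-13 points at r = 0.3, 8-10 at r = 0.5, 2-2.5 at r = 0.7 and under 0.5 at r = 0.8. The figures in the table therefore correspond to r = 0.5. The gain per outcome is also smaller if both effects are half as large: E/e' 25% → 28-29%, GLS about 30% → 32-33%. These points stand as limits on the size of the gain. They do not touch error control or the fact that no rejection is lost.

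A third objection is that, when only one effect is real, the error for the null outcome nearly doubles while power for the real effect hardly moves. This is correct, but that error stays within the 5% family-wise limit that the split already implies.

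**Conclusion.** The point holds, as a recommended efficiency gain. That Holm keeps family-wise error at or below 5% and retains every rejection is a mathematical fact and needs no assumption about the correlation between outcomes. The limit covers one prespecified test per coprimary outcome; it does not extend to the secondary, per-protocol or sex analyses.

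The size is illustrative. It is about 5-6 points for E/e', 3-4 for GLS and 8-10 for both, if both planned effects are real, 36 patients per arm are evaluable and the outcome correlation is 0 to 0.5. The inputs are the plan's own, and the assumed mean E/e' of 11.1 lies below the trial's entry cut-off of 13. The gain is close to nil if only one effect is real or if baseline and 3-month values are very highly correlated. The silence on whether one or both outcomes must be significant should be resolved in either case, because it determines which rule applies.

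**What to change.** Before unblinding, state in Section E whether each coprimary outcome can be claimed separately or both are required.

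- **If separately**, replace the coprimary part of the significance sentence with: *The two coprimary outcomes are tested with the Holm procedure at family-wise two-sided alpha 0.05 (smaller p at 0.025; if significant, the other at 0.05). 97.5% confidence intervals are reported for both.*
- **If both are required**, test each at two-sided 0.05 with no split.

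The sample-size calculation at 0.025 can stay as the conservative case.

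The cost is one or two sentences, with no extra patients, visits or measurements. There are two small downsides. Simultaneous intervals that match Holm exactly are less simple than 97.5% intervals, and a plain 97.5% interval can include zero for an outcome claimed at the second step; the report should say so if it happens. The second is the higher error for a null outcome when the other effect is real, as shown in the check. If the data are already unblinded, the fixed 0.025 rule should stand.

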performing the cytokine assays will be blinded to group assignment to ensure rigor. All assays will be run at the [name] Lab at the University of Oklahoma Health Sciences Center.

In addition, we will perform exploratory analyses in order to determine relationships between clinical and cytokine responses to LLTS and identify predictors of response based on baseline cytokine levels. It is known that vagus nerve stimulation attenuates inflammation through the cholinergic anti-inflammatory pathway^{12,14-17}. If this pathway is important in HFrEF as well, we expect that the decrease in cytokines will be correlated with the effect on echocardiographic markers of diastolic dysfunction and/or improvement in exercise capacity.

We intend to recruit 72 patients. Patients will be enrolled in the study over 15 months and the total duration of the study including follow-up will be 18 months, allowing for 3 months of startup and 3 months close-out. Patients will be followed with 3 outpatient visits (baseline, 1 month and 3 months). During the baseline visit, a complete history and physical examination will be done by one of the investigators. In addition, patients will be instructed on how to use the TENS device and attach the electrode clip on the respective site based on their randomization group, and will be asked to repeat the process themselves under direct supervision, to ensure correct use of the device. This process will be done by a clinical coordinator and/or physician who is unblinded to random allocation.

At each follow-up visit, patients will have a brief history and physical examination, and any cardiovascular events will be recorded. In addition, the discomfort threshold for tragus stimulation

will be obtained to ensure that patients are receiving adequate stimulation. Patients will undergo echocardiography at baseline and 3 months to assess diastolic function. A 6-minute walk test will be performed at baseline and 3 months to assess exercise capacity. A 5-min ECG and 10 second ECG will be performed at baseline and 3 months.

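### Power for 72 patients carries no loss allowance at the enrolment cap, leaving GLS no margin on its stated 90%; ANCOVA on the baseline already collected would gain power over the planned change-score test at no cost

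*Combined protocol and SAP*

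**What the plan says.** Section D (under Aim 2) gives the recruitment target: "We intend to recruit 72 patients". The Patient enrollment paragraph makes the same number a ceiling: "A maximum of 72 patients meeting the inclusion criteria and not meeting the exclusion criteria will be enrolled in the study".

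Section E, Sample size and power calculations, is open about its basis: "we have simplified the analysis to focus on the difference in" E/e' between the two arms. From a mean of 11.1 (SD 4.4) and a 30% reduction, "72 patients would provide 80% power to detect the specified effect sizes at a two-sided α level of 0.025". For GLS, with SD 2.2, the same number "would provide 90% power to detect an absolute 1.8% difference in GLS between the 2 groups". Neither statement mentions losses or says whether the 72 are enrolled or evaluable.

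On timing, Section D states that "Patients will undergo echocardiography at baseline and 3 months to assess diastolic function", and Definition of outcomes begins "The coprimary outcomes at 3 months are" before naming E/e' and GLS. The planned analysis in Section E is a "repeated measures ANOVA, with 2 time points (baseline, 3 months) and 3 terms included in the model": group, time and their interaction. Each coprimary outcome is tested at 0.025.

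**The concern.** The only post-baseline echocardiogram is at 3 months, so a patient who misses it has no post-baseline value for either coprimary outcome. With enrolment capped at 72, losses cannot be replaced. The stated power therefore needs nearly complete follow-up, which matters most for GLS.

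A second issue is separate from losses. With two time points, the group-by-time interaction is the comparison of mean change between arms. Its power depends on the correlation (rho) between the baseline and 3-month values, which the plan does not give. The actual power may be below or above that of the simplified two-group calculation. The plan also measures baseline in everyone but uses it in a less efficient way than it could. At stake is precision in a small study, not validity.

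**Working it through.** **Inputs from the plan (Section E).** Two-sided alpha 0.025, 1:1 allocation. E/e': difference 0.30 × 11.1 = 3.33, SD 4.4, standardised 0.757. GLS: difference 1.8, SD 2.2, standardised 0.818. Assumed here, because the plan gives neither: losses of 5%, 10% and 15% (68, 65 and 61 evaluable) and rho of 0.3 to 0.7.

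**Step 1: the plan's own figures.** Noncentrality is the standardised difference divided by √(1/n1 + 1/n2). With 36 per arm that is 0.757 × √18 = 3.21 for E/e' and 0.818 × √18 = 3.47 for GLS. The normal critical value is 2.241. Results are shown as t / normal approximation.

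| Evaluable | E/e' | GLS |
|---|---|---|
| 72 | 81.9 / 83.4% | 87.8 / 89.1% |
| 68 | 79.4 / 81.0% | 85.7 / 87.1% |
| 65 | 77.3 / 79.1% | 83.9 / 85.5% |
| 61 | 74.2 / 76.2% | 81.2 / 83.0% |

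The stated 90% for GLS is within rounding of its SD: an SD of 2.15 also prints as 2.2 and gives 89.4 / 90.5% at 72. Even then the normal approximation is 89.6% at 70 evaluable. By the t calculation GLS is 80.5% at 60 evaluable and 79.7% at 59, so it crosses 80% at the 13th loss.

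**Step 2: whether the E/e' column can be used.** Section G requires E/e' of at least 13 at entry, so no enrolled patient has the assumed mean at baseline. A 30% reduction from 13 is 3.9. With SD held at 4.4 (an assumption), power is 90-91% at 65 evaluable and 87-89% at 61. The fall below 80% in the table disappears.

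**Step 3: planned test against ANCOVA, GLS.** With equal SDs at both visits, the change score has variance 2(1 − rho)SD². ANCOVA has residual variance (1 − rho²)SD² and loses one degree of freedom. The ratio is (1 + rho)/2, that is 0.65, 0.75 and 0.85 at rho 0.3, 0.5 and 0.7. Power by the t calculation:

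| Evaluable | Test | rho 0.3 | rho 0.5 | rho 0.7 |
|---|---|---|---|---|
| 68 | interaction | 71% | 86% | 98% |
| 68 | ANCOVA | 89% | 94% | 99% |
| 65 | interaction | 69% | 84% | 97% |
| 65 | ANCOVA | 87% | 93% | 99% |
| 61 | interaction | 66% | 81% | 96% |
| 61 | ANCOVA | 85% | 91% | 98% |

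In a simulation with no treatment effect (rho 0.5, 8,000 runs) both tests rejected in 2.5% of runs.

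**Step 4: the same comparison for E/e', with the entry cut applied throughout.** Assume a normal distribution with mean 11.1 and SD 4.4, cut at 13. The baseline mean becomes 15.9 and the variance is multiplied by 0.280 (SD 2.33). The sham mean at 3 months is 11.1 + rho × (15.9 − 11.1), which is 12.54 at rho 0.3 and 13.50 at rho 0.5. Thirty per cent of these gives effects of 3.76 and 4.05. The change-score variance is 4.4² × [(1 − rho)² × 0.280 + (1 − rho²)], and the ANCOVA variance is 4.4² × (1 − rho²). At 65 evaluable:

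- rho 0.3: 85.5% (interaction) against 90.3% (ANCOVA), a gain of about 5 points.
- rho 0.5: 96.2% against 97.5%, a gain of about 1 point.

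**The case against.** The strongest reply is that the study was sized on E/e' at 80%, and GLS power was then reported for the same number. On that view 90% is a by-product, and against 80% GLS has room for about 12 losses. This stands: the missing margin is against the plan's own GLS statement, not a design failure.

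Losses and test choice are also different matters. Losing 7 patients costs about 4 points of GLS power (87.8% to 83.9%); most of the ANCOVA gain comes from replacing a valid test with a more efficient one. If rho is 0.6, the planned test already gives 91.5% for GLS at 65 evaluable. That stands too, so the benefit depends on a rho the plan does not give.

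Retention is partly addressed. Follow-up is short, and Section D encourages patients to return whatever their adherence. The adherence above 90% quoted there does not settle it: it concerns daily sessions in an atrial fibrillation study, not attendance at the 3-month echocardiogram.

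A reader might infer that the 80% and 90% are miscalculated; they reproduce within rounding. A reader might also infer that the trial is underpowered for E/e'. That rests on the 11.1 mean, which the entry criterion contradicts.

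**Conclusion.** The point holds as a costless improvement and a needed clarification, not as an error. The power statement has no loss allowance at a fixed cap, and GLS has no margin against its stated 90%: 88-89% with complete data and 84-85% with an assumed 10% loss. No E/e' shortfall is claimed.

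ANCOVA is at least as powerful as the planned interaction test at every rho examined. For GLS at 65 evaluable the gain is 19 points at rho 0.3 (87.4% against 68.8%), 9 at 0.5 and under 2 at 0.7. For E/e' it is about 5 points at 0.3 and 1 at 0.5. These sizes rest on assumed losses, an assumed rho and, for GLS, equal SDs at both visits. ANCOVA does not secure 90% in every case: GLS at 61 evaluable and rho 0.3 is 85%. It restores precision only and would not remove bias if the missing 3-month values are informative. The planned test remains valid, and type I error is not in question.

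**What to change.** Keep 72 patients.

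1. Make the primary analysis of each coprimary outcome an ANCOVA of the 3-month value on arm, baseline value and sex (the stratification factor). Include all randomised patients with a 3-month echocardiogram, in the arm assigned, each outcome tested at 0.025. Keep sex-by-arm terms as exploratory. Adding sex costs one degree of freedom, which changes GLS power at 65 evaluable by less than 0.1 point.
2. Restate power as that of 72 evaluable patients, with GLS at about 88-89% before adjustment for baseline. Name the formula, and show power for an assumed 5-15% loss and rho of 0.3-0.7. Reconcile the E/e' mean used for power with the entry criterion.

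A sensitivity analysis for missing 3-month values is good practice but optional; the point does not rest on it.

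The cost is a rewritten power paragraph and a sentence or two on the primary model. No extra patients, visits or measurements are needed. The stated GLS power becomes slightly less favourable before adjustment.
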